7.4.2 Baseline Assessments for Group 3 (Healthy Volunteer)

All baseline assessments for Group 3 will be the same as those for Groups 1 and 2 with the exception of Number 1 and 2. Healthy volunteers will not be required to give any (blood/urine) samples or have the DXA imaging.

If the MRI and DXA scans are on the same day for Groups 1 and 2, then the baseline visit will last for approximately 2.5 to 3 hours. However, if the MRI and DXA scans are on different days, then the baseline visit will last for approximately 1.5 to 2 hours and the DXA scan for approximately 1 hour. The baseline visit for Group 3 will last approximately 1.5 to 2 hours.

7.5. Subsequent Visits

For Groups 1 and 2, a follow up visit will take place 6 months after the baseline assessment.

Tests 1, 2, 3 and 4 from baseline assessment will be repeated in exactly the same way for both Group 1 and 2.

Repeat data collection (on intervening treatment and disease monitoring results, from hospital records) will be performed.

No subsequent data collection or assessment will be performed on Group 3 (Healthy volunteers) at 6 months, as the only purpose of their inclusion is to establish reproducibility and a normal range for experimental MR output data. Therefore, group 3 participation stops at the end of their baseline assessments.

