Participants in Groups 1 and 2 will undergo a further experimental MR scan, DXA imaging and bone biomarker blood tests at 6 months or at time of progression/relapse, whichever is sooner (but no sooner than 3 months after the initial investigations) to evaluate change in disease burden and bone loss. The reason participants in Group 2 will be rescanned at 6 months even if they have not progressed to myeloma and are not on therapy, is to address the following questions, 1. Can trabecular thinning progression be detected with time in MGUS patients whose paraprotein is stable or rising? 2. Reproducibility test: In

patients with a stable paraprotein, if assumed that trabecular thickness is stable or at most slightly worse over 6 months, is trabecular quantification reproducible over time?

In addition to this, all participants in Groups 1 and 2 will also be asked to complete the short questionnaire relating to the MRI and DXA imaging and the quality of life questionnaire for assessment of patient experiences of both imaging procedures, both at the first study appointment and at the 6 month follow up appointment. Standard of care clinical investigations will be repeated within NHS protocols if clinically indicated. Results of relevant NHS diagnostic investigations, clinical outcomes and survival data will be collected and stored.

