6.3. Exclusion Criteria

Exclusion Criteria (All Groups)

Those who are unable or unwilling to give informed consent

Women who may be pregnant, breast feeding or women of child-bearing potential who are unwilling
or unable to take sufficient precautionary measures will be excluded due to DXA imaging.

Exclusion Criteria (Groups 1 and 2)

- Signs of Spinal Cord Compression
- Patients with documented metastatic lesions from another type of malignancy
- Known contraindication for a MRI scan (see Appendix B: contraindications to MR scan), including unacceptable pain on lying flat for 1 hour.

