7.3.2 Screening Assessments

All screening study assessments must be completed before any study procedures are carried out.

The following assessments will be carried out in order to establish eligibility for the study for participants in Groups 1 and 2 only.

Medical History

Detailed history of myeloma/MGUS including; date of diagnosis, staging (International Staging System) and location(s) of bone disease as per standard of care should be recorded. Detailed description of all prior and ongoing diseases and disorders should be documented along with any myeloma or bone strengthening therapies that were received.

Particular Details on history of fractures, history of osteoporosis, bone pain and analgesia requirements should be documented. Details on use of radiotherapy or vertebral augmentation should be collected.

- Treatment History and Concomitant Medication(s)
 Details of treatment history and current concomitant medication including all medications,
 treatments and therapies used in the prior 4 weeks, as well as those currently being taken should be recorded.
- Physical Examination
 Physical examination including assessment of ECOG status (Group 1 only), height and weight should
 be recorded for all participants.
- Local Clinical Laboratory Evaluations
 - Biochemistry: Sodium, Potassium, Total Protein, Albumin, Adjusted Calcium, Bicarbonate, Magnesium, Phosphate, Urea, Creatinine, LFTs, CRP, LDH, Uric acid, Glucose, Creatinine Clearance
 - Immunology: Beta-2 microglobulin, paraprotein, quantitative immunoglobulins, serum free light chains
 - Haematology: haemoglobin, haematocrit, bilirubin, WBC, platelet count, neutrophils, lymphocytes
 - Bone marrow assessment (only Myeloma and Smouldering myeloma): bone marrow aspirate and trephine to confirm diagnosis of myeloma
 - Urine pregnancy test: for women of child bearing potential (WCP)

Participants in Group 3 will undergo the following screening assessments before any study procedures are carried out:

- Medical History
 - Detailed history of any relevant previous medical conditions and their treatments
- Physical Examination
 Physical examination of height and weight to be recorded

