7.4. Baseline Assessments

7. 4.1 Baseline Assessments for Groups 1 and Group 2

Once consent has been given, the first study appointment will be offered, within four weeks. This first study visit will include the MR imaging protocol, DXA scanning, bone biomarker blood/urine tests and completion of both questionnaires. These procedures are described in further detail below. An administrator will manage these attendance arrangements; however, participants will be required to make arrangements for transportation to and from the OCMR and NOC. Participants will be given the opportunity to claim back the travel expenses and details of how to do this is available in the Participant Information Sheet. Whenever possible, the administrator will try and arrange for the MRI and DXA scan to happen on the same day, should this not be possible and the scans are arranged for different days, the participants will have to attend an additional study visit.

- Blood and urine samples for bone turnover biomarkers total ALP, PINP and serum CTX1 (Vasikaran et al, 2011). This will require a morning fasted 20ml clotted (serum) blood sample to be taken. Additional experimental assays of biomarkers for myeloma bone disease will be performed on these samples at the Oxford University Hospitals NHS Foundation trust laboratory. This assessment will take approximately 10 minutes.
- 2. Body composition using whole body DXA (1 hour radiology appointment at the NOC (Nuffield Orthopaedic Centre)). Bone Mineral Density (BMD) will be measured by (DXA) using a study approved densitometer. BMD measurements will be made at the lumbar spine (L1-4), hip, whole body and an Instant Vertebral Assessment (IVA). If participants have already had a DXA scan at one of these sites within 2 months of the visit date, then that scan will be used and the scan will not be repeated for that site. This assessment will take approximately 50 minutes.

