7.6. Sample Handling

All participants will be assigned a unique study ID which will also be used to identify samples. All laboratory samples, will be anonymised to the research team for this study however, direct clinical care team will have access to identifiable information in order to create a report for clinical purposes to inform participants care.

Blood and urine samples for bone turnover biomarkers total ALP, PINP and serum CTX1 will be taken at baseline and follow up at 6 months for Groups 1 and 2; no samples will be obtained from participants in Group 3. This will require a morning fasted 20ml clotted (serum) blood sample to be taken. Additional experimental assays of biomarkers for myeloma bone disease will be performed on these samples at the Oxford University Hospitals NHS Foundation trust laboratory. All samples collected from Groups 1 and 2 at both baseline and follow up will be stored for the duration of the study to run analytes in parallel to limit batch wise processing. Samples collected for this study will not be stored for use in other research and will be destroyed after analysis. These samples will only be accessible to study staff and authorised personnel.

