13.7. Other Ethical Considerations

Any clinically significant incidental findings during testing of blood samples or during the scanning procedures (both MRI and DXA) will be reported to the CI and the CI will then report these to the patient and GP.

DXA:

DXA imaging entails a small exposure to radiation, equivalent of up to 21 days of background radiation for the duration of the study. The results of the lumbar spine, hip and vertebral fracture assessment will be made available to the patient's cancer care team for further clinical management. The Whole body

DXA will not routinely be reported on. Any incidental findings will be reported to the CI and the CI will then report these to the patient and GP.

MRI scan:

MRI safety checklist review will be conducted before admission into the scanner. Scan will last up to 60 minutes. Patients will be given sufficient non-sedating pain relief prior to the scan if required, and positioning will be optimised according to any potential chronic bone pain. If a patient finds lying in the scanner too uncomfortable despite pain relief, the procedure will be abandoned. MRI is safe and non-invasive and does not involve any ionising radiation (x-rays). No contrast injections will be given during the scan.

Blood sample collection:

Patient's skin will be prepped with an anti-septic wipe, which very rarely can cause a skin reaction. If a patient knows they are allergic to the anti-septic prep, another sterile agent will be used. They will then feel a sharp scratch as the needle is inserted and blood is drawn up into the sample bottles. It is exceedingly rare for blood tests to be complicated; however bleeding and infection are potential risks that will be minimised as much as possible by monitoring for bleeding after the test, and using sterile equipment and the sterile non-touch technique. All procedures will be carried out by appropriately trained healthcare professionals.

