17.1. APPENDIX A: Schedule of assessments

	Time of Assessments			
Type of Assessments	Baseline	6 months (or clinical relapse/progression)		
Clinical history & Examination (Routine assessment)	Х	х		
Bloods and urine biomarkers *	Х	X		
Experimental MRI protocol	Х	X*		
DXA */** (Lumbar Spine and Hip Whole Body and VFA)	х	х		
Quality of Life Questionnaire (EQ- 5D) *	х	х		
DWMRI/DXA Patient Experience Questionnaire *	Х	Х		

^{*}Not in healthy volunteers

All procedures will happen during haematology clinic visit except DXA and MRI scan, which will be arranged for separate appointments.

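### The plan tests for pregnancy once, at screening, because of DXA, but repeats DXA at about 6 months with no test scheduled before it

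*Combined protocol and SAP*

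**What the plan says.** Section 6.3 gives DXA as the reason for the pregnancy exclusion. It covers women who may be pregnant, and women of child-bearing potential unwilling "or unable to take sufficient precautionary measures will be excluded due to DXA imaging".

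Section 7.3.2 lists the only pregnancy test in the plan, among the eligibility assessments for Groups 1 and 2: "Urine pregnancy test: for women of child bearing potential (WCP)".

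Section 7.4 sets the time to the baseline visit: "Once consent has been given, the first study appointment will be offered, within four weeks". The four numbered baseline items are biomarker samples, DXA, MRI and questionnaires.

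Section 7.5 covers follow-up: "Tests 1, 2, 3 and 4 from baseline assessment will be repeated in exactly the same way for both Group 1 and 2". Section 5 places that visit at 6 months, or at progression or relapse if sooner, "but no sooner than 3 months after the initial investigations".

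Appendix A marks DXA at both time points and has no pregnancy-test row. Its urine row is for biomarkers. Section 13.7 states the DXA dose as "equivalent of up to 21 days of background radiation for the duration of the study".

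**The concern.** The protocol treats DXA in pregnancy as something to prevent, and it asks for a test as well as contraceptive precautions before the first scan. The second scan is the same exposure in the same women, yet the plan schedules no test before it. A negative result from screening says nothing about a pregnancy that began afterwards.

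A pregnancy that starts between the visits, and is unknown or undisclosed, could therefore be exposed at follow-up. This is a participant-safety and scheduling point. It does not touch the endpoints, the power calculation or the analysis.

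**Working it through.** The plan gives no figure of its own to reproduce. The check compares the two DXA visits and then does simple interval arithmetic.

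**Scheduled safeguards before each DXA**

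| | First DXA | Second DXA |
|---|---|---|
| Pregnancy test | 1 (7.3.2) | 0 (7.5, 8.2 and Appendix A list none) |
| Contraceptive precautions | Entry condition (6.3) | Same condition, not re-checked |
| Clinical history | Yes | Yes (Appendix A), no stated pregnancy enquiry |
| MRI form question on pregnancy | Self-report, reviewed before MRI (13.7) | Same |

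The instruction to repeat items 1 to 4 does not bring the pregnancy test in, because the test belongs to screening (7.3.2) and not to the baseline list (7.4.1).

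**Age of the screening test at each scan**

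Consent comes before any study investigation (7.1), so the test falls between consent and the baseline visit.

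- First DXA: up to 4 × 7 = 28 days, if the visit takes place within the four weeks in which it is offered.
- Second DXA, earliest: 3 × 30.4 ≈ 91 days, with the test done on the day of the baseline visit.
- Second DXA, at 6 months: about 183 days after baseline (365 / 2 = 182.5). Adding up to 28 days gives 183 + 28 = 211 days.

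**Number affected**

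Only Groups 1 and 2 have DXA: 34 + 13 = 47 participants. The documents do not say how many will be women of child-bearing potential. An assumed range of 0 to 5 gives 0% to 5/47 = 10.6%.

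**Dose**

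The stated maximum for the whole study is equivalent to 21 days of background radiation. If the two visits contribute equally, which is an assumption, the second contributes up to 21 / 2 = 10.5 days.

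**The case against.** The strongest reply is that the plan already has several layers of protection, so asking for a further test is a preference about stringency.

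- **Precautions.** Contraceptive precautions are an entry condition that looks forward to both scans. However, the plan requires a test in addition to them before the first scan, so it does not itself treat them as enough.
- **Discontinuation.** Section 7.7 names pregnancy, and ineligibility that arises during the study, as grounds for discontinuation, and bars further procedures after withdrawal. The plan thus foresees a pregnancy between visits, but this safeguard works only once the pregnancy is known.
- **MRI form.** It asks about possible pregnancy, and section 7.4.1 aims for MRI and DXA on the same day. This is real partial cover. It remains self-report and is tied to a scan at a different location. The DXA may also fall on another day, and the order of the two scans is not fixed.
- **Reuse of a recent DXA.** A scan from the previous 2 months replaces the study scan at that site, so not everyone has a full second exposure. A reused scan could also predate the screening test, so 28 days is not a firm limit at baseline. Both points stand, but they narrow the gap without closing it.
- **Unseen practice.** The DXA unit may run its own pregnancy check. Nothing in the documents says so.
- **Timing.** No document sets a maximum age for the test, so the timing asked for at follow-up is a judgement. That is fair.

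The low dose and the assumed numbers also stand, and they limit the weight of the point.

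**Conclusion.** The concern holds. One pregnancy test is scheduled before the first DXA and none before the second, although the hazard is the reason for the exclusion. At follow-up the only test is about 91 to 211 days old, against up to about 28 days at baseline.

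The consequence is minor. The dose is low, the affected women may number none (assumed 0 to 5 of 47), and no statistical quantity changes. The absence of a scheduled test is certain from the text. The number of women, the equal split of the dose and attendance within four weeks of consent are assumptions. The change is worth making because it costs almost nothing and applies the protocol's own safeguard to both exposures.

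**What to change.** In section 7.5 and Appendix A, add a urine pregnancy test for women of child-bearing potential in Groups 1 and 2 before the follow-up DXA. Record the result before the scan, and do not perform the DXA if it is positive.

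Run the test when the follow-up urine is collected and do not leave it to the laboratory, because section 7.6 says: "All samples collected from Groups 1 and 2 at both baseline and follow up will be stored for the duration of the study". Appendix A also notes: "All procedures will happen during haematology clinic visit except DXA and MRI scan, which will be arranged for separate appointments". Where the DXA is on a later day than the urine collection, do the test on the DXA day.

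The cost is one line in section 7.5, one row in Appendix A and one dipstick for each of an assumed 0 to 5 women, plus a fresh urine sample for any of them scanned on a later day. If no such women enrol, there is no running cost.

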7.6. Sample Handling

All participants will be assigned a unique study ID which will also be used to identify samples. All laboratory samples, will be anonymised to the research team for this study however, direct clinical care team will have access to identifiable information in order to create a report for clinical purposes to inform participants care.

Blood and urine samples for bone turnover biomarkers total ALP, PINP and serum CTX1 will be taken at baseline and follow up at 6 months for Groups 1 and 2; no samples will be obtained from participants in Group 3. This will require a morning fasted 20ml clotted (serum) blood sample to be taken. Additional experimental assays of biomarkers for myeloma bone disease will be performed on these samples at the Oxford University Hospitals NHS Foundation trust laboratory. All samples collected from Groups 1 and 2 at both baseline and follow up will be stored for the duration of the study to run analytes in parallel to limit batch wise processing. Samples collected for this study will not be stored for use in other research and will be destroyed after analysis. These samples will only be accessible to study staff and authorised personnel.

7.7. Discontinuation/Withdrawal from Study

Each participant has the right to withdraw from the study at any time. In addition, the Investigator may discontinue a participant from the study at any time if the Investigator considers it necessary for any reason including:

- Pregnancy
- Ineligibility (either arising during the study or retrospectively having been overlooked at screening)
- Significant protocol deviation
- Significant non-compliance with treatment regimen or study requirements
- Withdrawal of Consent
- Loss to follow up

For participants who are withdrawn from the study, identifiable data or tissue already collected with valid consent would be retained and used in the study. No further data or tissue would be collected or any other research procedures carried out on or in relation to the participant. All withdrawal information including reason for withdrawal will be recorded on the Withdrawal CRF.

Every effort will be made to replace participants who have been withdrawn from the study.

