1. SYNOPSIS

Study Title	The development and pilot testing of a new Magnetic Resonance (MR) imaging					
	protocol to quantify both myeloma disease burden and associated bone loss					
Internal ref. no. / short title	LOOMIS- myeLOma bOne MrI Study					
Study Design	Observational Prospective Cohort					
Study Participants	Group 1- Myeloma					
	Group 2- Monoclonal Gammopathy of Unco	ertain Significance (MGUS)				
	Group 3- Healthy Volunteers					
Planned Sample Size	60					
	Group 1- Myeloma- 34					
	Group 2- MGUS - 13					
	Group 3 - Healthy Volunteers - 13					
Planned Study Period	September 2017 – December 2021					
	Objectives	Outcome Measures				
Primary	To develop and pilot test a novel	Novel imaging based endpoints:				
	Magnetic Resonance (MR) imaging	1. DW-MRI (Diffusion Weighted-				
	protocol with the aim to accurately: 1. Quantify tumour burden	Magnetic Resonance Imaging): ADO (apparent diffusion coefficient)				
	2. Quantify bone loss	change (Pawlyn et al , 2016)				
	2. Quantity bone loss	2. Total spinal 'hole' volume				
		3. Total spine 'collapse' volume				
		4. FSA (Fine Structural Analysis):				
		trabecular wall thickness (Rafferty				
		et al, 2016)				
		Correlate endpoints:				
		Bone density (DXA imaging)Serum CTX-1				
		Serum P1NP				
		Further experimental serum				
		biomarkers of myeloma				
	bone disease					
Secondary	To pilot test a novel MR imaging protocol with the aim to accurately:	1 and 2 - Repeat quantification of endpoint parameters after induction				
	Detect longitudinal changes in	therapy and best response achieved				
	tumour load with therapy	by IWMG criteria or at treatment				
	2. Detect longitudinal changes in	failure				
	bone microarchitecture with					
	therapy					
	3. Assess participants Quality of					
	Life (EQ-5D) throughout the					
	study					

4.	Assess participants experience of	3 – Analyse participants quality of
	the novel MR imaging scan	life using data from the EQ-5D-5L
		questionnaire
		4- Analyse participants experience
		of the novel MR imaging using data
		from MRI/DXA scanning
		questionnaire

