10. STATISTICS AND ANALYSIS

10.1. Description of Statistical Methods

The primary outcome of this study is the ADC in patients with and without a complete/very good partial response to therapy at follow-up. It is estimated that for group 1, between baseline and follow-up, 85% of individuals will reduce their myeloma burden from 40% to 10% or less compared with 15% who will achieve a partial response (a ratio of 0.15).

A previous study in a similar population the median ADC score improved from 0.79 (IQR 0.66 to 1.26) to 1.5 (IQR 0.88 to 1.83) in those with a complete/very good partial response compared with 0.66 (IQR 0.52 to 0.87) to 0.75 (0.51 to 1.27) in those with a partial response [Latifoltojar BJH 2016].

To detect a similar difference in this cohort with an ADC in complete/ very good partial response of 1.5 at follow-up vs. 0.75 in those with a partial response, a conservative estimated SD of 0.5, and a ratio of 0.15 will require 34 individuals in total (29 vs. 5) with 80% power and 0.05 type I error. We will, therefore, aim to recruit a total of 37 (31 vs. 6) participants for the study to allow for a dropout rate of 5%.

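### Section 7.7 lets non-compliance with a treatment the study does not assign end participation, which can lose follow-up data from the stratum of about 5

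*Combined protocol and SAP*

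**What the plan says.** The Synopsis describes the design as "Observational Prospective Cohort". The only interventions in section 8 are the MRI and DXA scans. Under section 7.5, information on intervening treatment is taken from hospital records.

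Section 7.7 covers leaving the study:

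- **Who decides.** The rule is permissive: "the Investigator may discontinue a participant from the study at any time if the Investigator considers it necessary for any reason including". A list of reasons follows.
- **The ground at issue.** One listed reason is "Significant non-compliance with treatment regimen or study requirements". Study requirements are named separately from the treatment regimen.
- **Data before withdrawal.** Kept: "identifiable data or tissue already collected with valid consent would be retained and used in the study".
- **Data after withdrawal.** None: "No further data or tissue would be collected or any other research procedures carried out on or in relation to the participant".
- **Replacement.** "Every effort will be made to replace participants who have been withdrawn from the study".

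Section 10.1 defines the primary outcome as ADC at follow-up in patients with and without CR/VGPR. It expects an 85:15 split and sizes the comparison at 34 (29 vs. 5), raised to 37 (31 vs. 6) for 5% dropout. Section 10.2 gives no analysis set, no missing-data method and no rule for withdrawn or replaced participants.

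**The concern.** The protocol sets no regimen to comply with. Because study requirements are named separately, the natural reading of the clause is the patient's own anti-myeloma therapy. Deviating from that therapy happens after baseline and may lie on the path to response. An observational study of response has no evident need to remove a patient for it.

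The retained baseline data do not rescue the primary outcome, which needs ADC and response status at follow-up. The early follow-up scan at progression or relapse in section 5 does not help someone already withdrawn, since section 7.7 stops all research procedures.

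The stake is highest in the small stratum, where one participant in five is 20% of the information. A replacement comes from the recruited population, of whom the plan expects 85% to reach CR/VGPR. Replacement therefore restores the total but usually not that stratum. If those withdrawn tend to respond less well, the pooled change from baseline to follow-up and the observed response mix could also look more favourable than in the patients recruited.

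**Working it through.** **Inputs, all from section 10.1.** Follow-up ADC means 1.5 and 0.75, so the difference is 0.75; SD 0.5; small-to-large ratio 0.15; type I error 0.05; power 80%. Sidedness is not stated. Two-sided is used because it reproduces the plan's figure and one-sided does not (25 to 26 in total).

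**Reproducing the plan's size.** For a two-sample t test, the standard error is SE = 0.5 × √(1/n1 + 1/n2) and the noncentrality is 0.75/SE, with n1 + n2 − 2 degrees of freedom. Power comes from the noncentral t distribution. With n2 = 0.15 × n1 left unrounded:

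- n1 = 28, n2 = 4.20: power 79.2%
- n1 = 29, n2 = 4.35: power 80.7%

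The first to pass 80% is n1 = 29. Rounding 4.35 up to 5 gives 29 + 5 = 34, as stated. Inflating each stratum for 5% dropout gives 29/0.95 = 30.5, so 31, and 5/0.95 = 5.3, so 6. The total is 37, as stated.

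**Effect of losing participants from the small stratum**, same difference and SD:

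| Scenario | n1 vs. n2 | SE | Noncentrality | Power |
|---|---|---|---|---|
| As sized | 29 vs. 5 | 0.242 | 3.10 | 85.2% |
| One lost, not replaced | 29 vs. 4 | 0.267 | 2.81 | 77.8% |
| One lost, replaced by a CR/VGPR patient | 30 vs. 4 | 0.266 | 2.82 | 78.0% |
| As inflated for dropout | 31 vs. 6 | 0.223 | 3.36 | 90.5% |
| One lost from 31 vs. 6, replaced by a CR/VGPR patient | 32 vs. 5 | 0.240 | 3.12 | 85.8% |
| Two lost from 31 vs. 6, both so replaced | 33 vs. 4 | 0.265 | 2.83 | 78.7% |

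For the first row: 0.5 × √(1/29 + 1/5) = 0.242 and 0.75/0.242 = 3.10.

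Stress cases from 29 vs. 5, with two or three of the five lost and replaced by CR/VGPR patients, give 67.2% (31 vs. 3) and 51.4% (32 vs. 2).

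**What replacement does.** Comparing 29 vs. 4 (77.8%) with 30 vs. 4 (78.0%), replacement neither causes the loss of power nor repairs it. The loss comes from the small stratum. On the 85:15 split, the chance that one replacement falls in that stratum is about 15%.

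**Which starting point applies.** The Synopsis and sections 5 and 6.1 set Group 1 at 34, while section 10.1 aims for 37. At 34 there is no dropout allowance, and one loss from the small stratum takes power just below 80%. At 37 it takes two. That conflict is a separate matter, but it determines which rows apply.

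**The case against.** The strongest reply is that this is loose wording with no demonstrated consequence.

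- **The rule is discretionary.** Correct. Neither withdrawal nor replacement is automatic, and since no regimen is set, the clause may be used only for study requirements. The loss is possible, not certain.
- **No link between compliance and response is given.** Correct. The documents give no non-compliance rate either. Stopping therapy on a clinician's decision is also not obviously non-compliance.
- **Progressing patients are scanned early.** Section 5 brings follow-up forward to progression or relapse, though no sooner than 3 months after the initial investigations, and poor response is not itself a withdrawal ground. This narrows who could be lost but does not recover anyone already withdrawn.
- **The power losses are stress cases.** Largely correct. They place every loss in the small stratum, whereas the plan allows 5% dropout from all causes (0.05 × 34 = 1.7 participants across both strata). Any dropout from that stratum would cost the same. This clause adds an avoidable route to it.

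A reader might infer that the clause selects the cohort on its outcome and so biases the primary comparison. The documents do not support that. The clause selects on compliance. A changed mix of strata costs precision but does not by itself bias the ADC difference between strata; bias would need selection on ADC within a stratum, which nothing in the documents shows. A reader might also take 67% or 51% as the expected power. Those figures assume that two or three of the five are withdrawn, and the documents do not say how many would be.

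**Conclusion.** The point holds as a minor one. Section 7.7 contains a withdrawal ground that does not fit an observational study. Using it would discard the follow-up ADC and response data needed for the primary outcome, for a reason that may be related to response.

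The effect that can be sized is precision. One loss from the small stratum costs about 7 percentage points of power from 29 vs. 5 (85.2% to 77.8–78.0%), or about 5 points from 31 vs. 6 (90.5% to 85.8%). These figures are illustrations, not forecasts. They rest on the plan's difference of 0.75 and SD of 0.5, a two-sided 0.05 test, and the assumption that the withdrawn participant would have been without CR/VGPR.

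A more favourable pooled change and response mix is plausible if non-compliant patients respond less well, but its size cannot be computed from the documents.

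**What to change.** In section 7.7, remove the treatment-regimen wording from the reasons for study withdrawal and keep study requirements, so that deviating from therapy does not by itself end participation. State that such participants keep the scheduled follow-up MRI and response data collection unless they withdraw consent or cannot be scanned. In sections 7.7 and 10.2, state that replacements are reported and analysed in addition to withdrawn participants, not in their place, and that both appear in the participant flow.

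The cost is a wording amendment and a few follow-up scans that would otherwise be skipped. Those scans are already in the Appendix A schedule; the documents give no scan budget, so their funding should be confirmed. The change concerns study retention and analysis only, not any patient's treatment.
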